Upon completion of treatment Period 2 (Week 48) of the core study, Investigators will use their clinical judgment to decide if it is beneficial for participants to continue with the extension study. All participants will be considered for participation in the extension study. A new Informed Consent must be signed before proceeding into the extension study. The participant should provide their informed consent prior to the start of the Week 60 assessments of the core study.

[figure not shown]
The treatment will be offered in PFS in the extension study. This is a change from the core study, which used s.c. injections prepared from vials. During the treatment period, 25 treatment administration visits are planned, including a weekly loading regimen (Week 60E1, Week 61, Week 62) at the start of the treatment period.

All participants enrolled in the extension study will receive a weekly loading regimen (Week 60E1, Week 61, Week 62) at the start of the treatment period followed by a s.c. maintenance regimen (600 or 300 mg s.c. every 2 weeks (Q2W)). One administration equals two s.c. injections. Refer to [Section 4.2](#) for more details on dosages of the weekly loading regimen in both arms.

To maintain extension study blinding until final database lock of the core study, an Interactive Response Technology (IRT) algorithm will be used to re-assign participants to either iscalimab 600 mg (Arm 1) or 300 mg (Arm 2) s.c. Q2W in the extension study using ESSDAI (Cohort 1 and Cohort 2) and ESSPRI (Cohort 2) scores from predefined time points (Week 4 (or Week 0 if a score is missing at Week 4) and Week 48 (or Week 40 if a score is missing at Week 48)) in the TWINSS core study (refer to [Section 6.1.3](#) for further details).

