6.1.3 Treatment arms/group

No re-randomization is planned for the extension study. The treatment re-assignment for the extension study occurs at visit Week 60E1 which is the last visit of the core study (Week 60). Upon completion of the core study, Investigators will use their clinical judgment including responder definitions provided below to decide if it is beneficial for participants to continue with the extension study based upon response to therapy at the end of the treatment period of the core study.

Participants will be re-assigned to one of the following two treatment arms:

- Arm 1 - Iscalimab 600 mg s.c. Q2W
- Arm 2 - Iscalimab 300 mg s.c. Q2W

At Week 60 of the TWINSS core study, all eligible participants from the core study can opt to be enrolled in the extension study via IRT. The Week 60E1 visit will be performed on the same day once the Week 60 visit of the core study is completed by the participant. The Investigator or his/her delegate will contact the IRT after confirming that the participant fulfills all the extension study inclusion/exclusion criteria. An IRT algorithm will be programmed to assign the participant to blinded treatment in the extension study using ESSDAI (Cohort 1 and Cohort 2) and ESSPRI (Cohort 2) assessment scores from predefined time points in the TWINSS core study.

- For participants rolling over from Cohort 1 in the TWINSS core study, the change in ESSDAI score between Week 4 and Week 48 will be used to determine if the participant responded to treatment in the core study. If an ESSDAI score is missing at Week 4 and/or Week 48, then Week 0 or Week 40 scores should be respectively used for the algorithm. A decrease of 3 points or more from Week 4 (or Week 0 if the ESSDAI score is missing at Week 4) will classify the participant as a treatment responder in Cohort 1.

- For participants rolling over from Cohort 2 in the TWINSS core study, a change in both ESSDAI and ESSPRI scores between Week 4 and Week 48 will be used to determine if the participant responded to treatment in the core study. If an ESSDAI or ESSPRI score is missing at Week 4 and/or Week 48, then Week 0 or Week 40 scores should be respectively used for the algorithm. A decrease of 1 point or more in both the ESSDAI and ESSPRI scores from Week 4 (or Week 0 if the ESSDAI or ESSPRI score is missing at Week 4) will classify the participant as a treatment responder in Cohort 2.

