6.7.2 Instruction for prescribing and taking study treatment

All kits of study treatment assigned by the IRT will be recorded in the IRT system.

Study treatment (iscalimab 600 mg and 300 mg) will be administered s.c. by the participant, caregiver or site staff. The PFS will be provided by the site staff to the participant, who will self-administer the injections at the specified study time point. Participants will be instructed in detail how to self-administer the s.c. injection using the PFS. Site staff will administer the injection to those participants who are not able or unwilling to self-administer the PFS injection. Detailed instructions on the self-administration of the study treatment will be described in the IFU and provided to each participant. It shall be recorded on the corresponding eCRF(s) whether the participant self-administered the PFS or whether site staff or caregiver administered the PFS and whether it was administered at home or at the site.

Iscalimab 600 mg s.c. Q2W

- Iscalimab loading doses will be 600 mg s.c. (2 injections of 300 mg/2 mL) on Week 60E1 (Day 421), Week 61 (Day 428) and Week 62 (Day 435)
- From Week 62 the participant will receive 600 mg s.c. Q2W iscalimab until Week 106 (last dose)

Iscalimab 300 mg s.c. Q2W

- Iscalimab loading doses will be 600 mg s.c. (2 injections of 300 mg/2 mL) on Week 60E1 (Day 421), 300 mg s.c. (1 injection of 300mg/2 mL and 1 injection of 2 mL of the placebo) on Week 61 (Day 428) and 300 mg s.c. Week 62 (Day 435)
- From Week 62 the participant will receive 300 mg s.c. Q2W iscalimab until Week 106 (last dose)

The first study treatment administration will occur at Week 60E1 after the inclusion/exclusion criteria have been confirmed, all study scheduled assessments have been performed and the scheduled blood samples have been drawn. For the loading doses on Week 60E1 (Day 421), Week 61 (Day 428) and Week 62 (Day 435), all injections will be self-administered by the participant at the study site under the supervision of a site staff member after the study assessments for the visit have been completed. Participants will be required to attend the study site for the Week 64 visit and starting at Week 66, the participants will be allowed to self-administer the study medication at home on an alternating basis through to Week 106 or continue to present at the study site for injection administrations, based on the participant's preference and the investigator's judgment.

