^X Assessment to be recorded in the clinical database or received electronically from a vendor

¹ Corresponds to the Week 60 visit of the core study. Assessments carried out as part of Week 60 as per core study protocol should be used for Week 60E1 of the extension study.

² Optional site visits - Week 66, 70, 74, 78, 82, 86, 90, 94, 98, 102, 106. Participants who are unable to self-administer the PFS injections at home will visit the site and site staff will supervise self-administration or administer the PFS injection for them. Other participants who can self-administer the PFS injection can do so at home at these optional visits.

³ Informed consent should be obtained before commencement of the Week 60 assessments of the core study.

⁴ Contact IRT for new treatment reassignment.

⁵ AEs/SAEs occurring after the participant has signed the informed consent must be captured on the appropriate eCRF page.

⁶ C - These assessments shall be conducted as part of the core study CCFZ533B2201 and will not be repeated in this extension study

⁷ S - Assessment to be recorded in the source documentation only

⁸ [REDACTED]

⁹ Local lab testing of CMV IgG, IgM and DNA (by PCR) must be performed every 3 months until end of study. Hepatitis B monitoring applicable to HBsAg (-) patients who were HBcAb (+) and HBV DNA (-) at screening during the core study. Local lab testing of HBsAg and HBV DNA must be performed every 3 months until end of study.

¹⁰ While on treatment, coagulation monitoring applies only to participants who have antiphospholipid antibodies (lupus anticoagulant, anti-cardiolipin antibodies) and/or who are on pre-existing antithrombotic therapy/prophylaxis, as reflected in the exclusion criteria of the TWINSS core study protocol.

¹¹ Analysis of cryoglobulins will be done only for participants who were positive at screening in the TWINSS core study.

¹² Urine pregnancy tests will be performed throughout the study

¹³ Blood sample is collected pre-dose.

¹⁴ [REDACTED]

¹⁵ [REDACTED]

¹⁶ Optional [REDACTED]

¹⁷ [REDACTED]

¹⁸ [REDACTED]

¹⁹ In case of premature discontinuation, participants will enter the follow-up after completing assessments for this visit.

²⁰ Mandatory to all participants, including those who have discontinued the study prematurely.

²¹ Week 106 is the last dose administration visit in the Treatment Period.

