12.4.2 Statistical model, hypothesis, and method of analysis

Only descriptive statistics will be provided, no inferential statistics will be conducted.

Adverse events:

Treatment emergent adverse events (TEAEs) will be summarized. Only primary paths within MedDRA will be considered for AE reporting. The definition for “treatment emergent” is as follows:

- Events started on or after the first dose of study treatment or events present prior to the first dose of study treatment but increased in severity based on preferred term;
- AEs observed four weeks after last study-drug administration will not be considered as treatment-emergent

AEs will be summarized by presenting, for each treatment group, the number and percentage of participants having any AE, having an AE in each primary system organ class and having each individual AE (preferred term). Summaries will also be presented for AEs by severity and for study treatment related AEs. If a participant reported more than one AE with the same preferred term, the AE with the greatest severity will be presented. If a participant reported more than one AE within the same primary system organ class, the participant will be counted only once with the greatest severity at the system organ class level, where applicable.

SAEs will also be summarized.

Separate summaries will be provided for deaths, SAEs, and other significant AEs leading to discontinuation.

All AEs including non-treatment emergent AEs will be listed.

Laboratory data:

The summary of laboratory evaluations will be presented for two groups of laboratory tests (hematology and serum chemistry). Descriptive summary statistics for the change from baseline to each study visit will be presented. These descriptive summaries will be presented by laboratory test and treatment group. Change from baseline will only be summarized for participants with both baseline and post-baseline values. For each parameter, the maximum change from baseline will be analyzed analogously. Number and percentage of participants with notable abnormalities will be summarized.

Vital signs:

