Full Analysis Set (FAS): The FAS comprises all participants to whom study treatment for the extension study has been assigned by the re-assignment algorithm. For analysis on FAS, participants will be analyzed according to the treatment group to which they have been assigned. Only data in the extension study will be included in the analysis.

Summaries of extension data in FAS will be based on the core study cohort assignment and reassigned treatment groups.

- Cohort 1 CFZ533 600 mg
- Cohort 1- CFZ533 300 mg
- Cohort 2 CFZ533 600 mg
- Cohort 2 CFZ533 300 mg

Safety Set (SAF): The Safety Set includes all subjects who received at least one dose of study treatment. Subjects will be analyzed according to the actual treatment received. The safety set will be used in the analysis of all safety variables.

The actual treatment received in a period is defined as the treatment dose level (including loading dose) that a subject was most frequently exposed to during the period. The frequency will be calculated using data collected on the Dose Administration Record (DAR). In case a subject is exposed to more than one dose level for the same number of times during a period, the actual treatment is the earliest one administered to the subject in that period.

Summaries of extension data in SAF will be based on the re-assigned treatment groups.

- CFZ533 600 mg
- CFZ533 300 mg

The PK Set (PKS) includes all subjects who received at least one dose of iscalimab treatment and have quantifiable PK measurements of iscalimab. Analysis of plasma PK, will be based on PKS and by the iscalimab treatment dose level a subject is most frequently exposed to, including the loading dose, during the study. Only data in the extension study will be included in the analysis.

Summaries of extension data in PKS will be based on the re-assigned treatment groups.

- CFZ533 600 mg
- CFZ533 300 mg

The IM Set (IMS) includes all subjects who received at least one dose of iscalimab treatment and have quantifiable immunogenicity measurements of iscalimab. Analysis of immunogenicity data will be based on PKS and by the iscalimab treatment dose level a subject is most frequently exposed to, including the loading dose, during the study. Only data in the extension study will be included in the analysis.

Summaries of extension data in IMS will be based on the re-assigned treatment groups.

- CFZ533 600 mg
- CFZ533 300 mg

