2.4 Safety analyses

All safety endpoints (i.e., adverse events, laboratory data, and vital signs in extension study will be summarized by treatment for all subjects of the safety set.

Adverse events (AEs)

All adverse events in extension study are summarized based on treatment emergent only. The definition for "treatment emergent" is as below:

TEAE includes all events up to the last dose date plus 14 weeks (98 days) or the end of the entire study period (including the safety follow-up period), whichever occurred earlier. A listing of all adverse events during the study will be produced, with those defined as TEAE for the study treatment period with "treatment emergent" flag displayed.

The number and percentage of patients with treatment emergent adverse event (TEAE) will be summarized for the following:

- by treatment, primary system organ class and preferred term
- by treatment, primary system organ class, preferred term and maximum severity
- by treatment, Standardized MedDRA Query (SMQ) and preferred term.

Summaries will also be provided for study treatment related adverse events, serious adverse events, treatment related serious adverse events, deaths, and adverse events leading to permanent discontinuation of study-drug.

If a particular AE 'severity' is missing, this variable will be listed as missing and treated as missing in summaries. If a subject reported more than one adverse event with the same preferred term, the adverse event with the greatest severity will be presented. If a subject reported more than one adverse event within the same primary system organ class, the subject will be counted only once with the greatest severity at the system organ class level, where applicable.

The most common adverse events reported ($\geq 5\%$ in any group for each preferred term in the table by PT or $\geq 5\%$ in any group for each SMQ table) will be presented in descending frequency according to its incidence in all subjects starting from the most common event.

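### SAP 4.2 replaces the protocol's notable-laboratory limits without declaring it, so the counts for high white cells and high platelets drop out; secondarily, the SAP's TEAE definition has no start rule

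*SAP*

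**What the plan says.** **Laboratory values.** Routine hematology and chemistry results are primary endpoints in both documents. Protocol Section 8.4.1 refers to Section 16.1 (Table 16-1) for what counts as clinically notable. For laboratory data, protocol Section 12.4.2 states: "Number and percentage of participants with notable abnormalities will be summarized". SAP Section 2.4.3 plans the same kind of count but takes the parameters and limits from SAP Section 4.2. It adds shift tables by CTCAE grade (Table 2-3). SAP Section 3, as published, lists one departure from the protocol, a broader TEAE definition, and does not mention laboratory limits.

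**Creatinine clearance.** Protocol Table 8-3 specifies the MDRD formula. SAP Section 4.2 has a criterion based on Cockcroft-Gault.

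**Adverse events.** Protocol Section 12.4.2 treats as emergent "Events started on or after the first dose of study treatment or events present prior to the first dose of study treatment but increased" (the increase being one of severity), and closes the window four weeks after the last dose. SAP Section 2.4 says instead: "TEAE includes all events up to the last dose date plus 14 weeks (98 days) or the end of the entire study period", whichever is earlier. It gives no condition on onset or worsening.

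**The concern.** A count of participants beyond a limit depends on the limit. If the SAP uses other limits than the protocol, the promised table becomes a different table, and a reader of Section 3 would not know. Limits that became more sensitive lose no one. The trouble lies with limits that vanish, move to another scale, or are merged into a wider category from which the protocol's count cannot be extracted. Change-from-baseline summaries would still show an extreme rise through their maximum, but not how many participants crossed the limit.

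For adverse events, collection starts at consent: "AEs/SAEs occurring after the participant has signed the informed consent must be captured on the appropriate eCRF page" (protocol Table 8-1, footnote 5). Read literally, the SAP would count an event between consent and first dose as treatment-emergent under the dose later received, because in the Safety Set "Subjects will be analyzed according to the actual treatment received". If a programmer instead assumes a Day 1 start, nothing in the SAP says that an earlier event which worsens after dosing is to be kept. TEAE incidence is a primary endpoint, and the same definition feeds the registry tables in SAP Section 2.4.1.

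**Working it through.** **1. Laboratory limits side by side.** Inputs are protocol Table 16-1, SAP Section 4.2 and SAP Table 2-3. Only limits visible in both documents, plus all of hematology, are compared. Item 8 of the SAP biochemistry list is blank in the public text, so other chemistry limits are left out. The SAP hematology list runs from 1 to 6 without a gap.

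| Parameter | Protocol Table 16-1 | SAP 4.2 | Can the protocol count be recovered? |
|---|---|---|---|
| ALT, AST | ≥3 × ULN | ≥3 × ULN | Unchanged |
| Low platelets | <50 × 10⁹/L | CTC Grades 1–4 | Yes, Grade 3 boundary <50 |
| Low white cells | ≤2.0 × 10⁹/L | CTC Grades 1–4 | Yes, Grade 3 <2, apart from equality |
| Low neutrophils | ≤1 × 10⁹/L | CTC Grades 1–4 | Yes, Grade 3 <1, apart from equality |
| Bilirubin | ≥3 × ULN | any elevation; >2 × ULN | Yes, Table 2-3 Grade 3 >3 ×, apart from equality |
| GGT | ≥5 × ULN | >3 × ULN | Yes, Table 2-3 Grade 3 >5 ×, apart from equality |
| Hemoglobin | <7 g/dL = 70 g/L | <100 g/L or fall ≥20 g/L | No, Table 2-3 Grade 3 is <80 g/L |
| Creatinine | ≥3 mg/dL | ≥3 × ULN | Depends on ULN |
| Lymphocytes | ≤1 × 10⁹/L | <LLN | Depends on LLN; Table 2-3 cuts at 0.8, not 1.0 |
| Eosinophils | ≥12% | absolute ≥2.5 ×, ≥3 × ULN | Depends on ULN and white cell count |
| High white cells | ≥16 × 10⁹/L | none | No |
| High platelets | ≥700 × 10⁹/L | none | No |

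ALT and AST share a row, so there are 13 limits: 2 unchanged + 3 broader with a matching Grade 3 boundary + 2 broader and recoverable from Table 2-3 + 1 broader and not recoverable + 3 on another scale + 2 absent = 13. Table 16-1 has three high-side hematology limits (white cells, platelets, eosinophils). SAP 4.2 keeps one, on a different scale. Table 2-3 names only decreases for white cells and platelets.

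**2. The three limits on another scale.** The documents give no reference ranges, so those below are assumptions.

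- Creatinine, ULN 0.8 to 1.3 mg/dL: the SAP limit is 3 × 0.8 = 2.4 to 3 × 1.3 = 3.9 mg/dL, against 3.0. Cases are gained when ULN is below 1.0 and lost when it is above.
- Lymphocytes, LLN 0.8 to 1.2 × 10⁹/L: at 0.8, values from 0.8 to 1.0 are lost. At 1.2, values above 1.0 and below 1.2 are gained.
- Eosinophils, ULN 0.4 to 0.6 × 10⁹/L: the lower SAP limit is 2.5 × 0.4 = 1.0 to 2.5 × 0.6 = 1.5 × 10⁹/L. A share of 12% reaches it only if white cells are at least 1.0/0.12 = 8.3 to 1.5/0.12 = 12.5 × 10⁹/L. At 12% with fewer white cells, a participant is notable under the protocol but not under the SAP.

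**3. TEAE window.** The SAP's own figure reproduces: 14 × 7 = 98 days. The last dose is at Week 106, Day 743, and 743 + 98 = 841, the Week 120 day. The protocol window ends at 743 + 28 = Day 771. From first dose on Day 421, the protocol window is 771 − 421 + 1 = 351 days. The SAP window with the same start would be 841 − 421 + 1 = 421 days. The extra 70 days are enough to explain why Section 3 calls the definition broader. That word therefore does not tell the reader that the onset and worsening condition is missing.

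**4. Room for pre-dose events.** Protocol Section 3: "The participant should provide their informed consent prior to the start of the Week 60 assessments of the core study". Section 6.1.3: "The Week 60E1 visit will be performed on the same day once the Week 60 visit of the core study is completed". Section 6.7.2: "The first study treatment administration will occur at Week 60E1 after the inclusion/exclusion criteria have been confirmed, all study scheduled assessments have been performed". Pre-dose events are possible, but the gap will usually be part of one day, although the consent date itself is not fixed. For scale, if all 206 enrolled participants (SAP Section 1.1) are dosed, each one whose only event is pre-dose adds 1/206 = 0.49 percentage points overall. Within one arm it adds more, but the documents do not give arm sizes.

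**The case against.** The strongest reply has five parts.

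- **The TEAE gap is nominal.** SAP Section 2.4 restricts summaries to events in the extension study and ties the flag to its treatment period, which begins at Week 60E1. Day 1 and post-baseline are anchored to the first extension dose, conditions present at consent go to medical history (protocol Section 10.1.1), and any error over-counts. Most of this stands, so the TEAE part is secondary. A reader might infer that TEAE incidence would be materially inflated; the same-day visits do not support that.
- **More sensitive limits are ordinary refinement.** This stands for bilirubin, GGT, and low platelets, white cells and neutrophils, where the protocol's count is recoverable. It does not answer the two absent limits, the three on another scale, or hemoglobin.
- **Table 16-1 may not bind the analysis.** Protocol Section 12.4.2 does not cite it, and Section 10.1.1 calls its contents alert ranges. But Section 8.4.1 points to it for notable findings, and Section 16.1 says its criteria define notable abnormalities. SAP Table 2-5 repeats its blood-pressure limits, and SAP Table 2-2 foresees a patient with both a notably high and a notably low value in one window. No parameter visible in SAP 4.2 has both a high and a low limit.
- **The public SAP is incomplete.** Table 2-4 and Section 2.6 are not visible, item 8 is blank, and the CTCAE list ends with an open-ended reference to other parameters. The conclusion must therefore be limited to the visible text. A reader might infer that potassium, glucose or alkaline phosphatase limits were also dropped; item 8 prevents that conclusion. The unbroken hematology list gives no such reason for the two missing limits.
- **Safety detection is not lost.** The protocol relies on hematology monitoring for lymphoproliferative disorder and thrombosis (Table 4-1), and a reader might infer that signals for these would be missed. The documents do not support this. They name neither limit as a marker, they add physical examination and coagulation tests, and clinically significant values must be reported as adverse events.

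**Conclusion.** The point holds, at minor to moderate weight. On the visible text, SAP 4.2 substitutes its own notable-laboratory limits for those of Table 16-1 and Section 3 does not say so. Of 13 comparable limits, 7 are unchanged or recoverable and 6 are not reliably recoverable: high white cells and high platelets (absent), hemoglobin below 70 g/L (merged into a wider category), and creatinine, lymphocytes and eosinophils (another scale). For those last three, the direction of gain or loss rests on assumed reference ranges. The calculation shows that cases can move, not how many will.

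The loss is of a promised descriptive summary of a primary endpoint. The study plans no inferential analysis, so no test result changes. The TEAE definition is incomplete as written, with an effect probably close to zero. The creatinine-clearance mismatch is real, but Table 16-1 has no clearance criterion, so it alters no count that the protocol promised.

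**What to change.** - **SAP 4.2:** keep the current criteria and add six rows labelled as protocol Table 16-1: high white cells, high platelets, creatinine, lymphocytes, eosinophils and hemoglobin below 70 g/L. Bilirubin, GGT and the three low-side counts need no new row.
- **SAP 2.4:** add that a TEAE has its onset on or after the first extension dose, or was present before it and increased in severity after it. Keep the current end rule.
- **Creatinine clearance:** reconcile the formula between protocol Table 8-3 and SAP 4.2.
- **SAP 3:** list the remaining departures from Table 16-1 with reasons, and say that the TEAE change concerns the end of the window.

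The cost is one clause, six table rows and a few lines of text. The laboratory data and event dates are already collected. The downside is slightly longer tables with two labelled sets of criteria.
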